3 STUDY DESCRIPTION

3.1 Summary of Study Design

This is a Phase 2, randomized, double-blind, placebo-controlled, parallel-group, multicenter, dose escalation and proof-of-concept study to evaluate the safety and efficacy of razuprotafib, administered three times daily (TID) (every 8 hours [Q8H]), in hospitalized subjects with moderate to severe COVID-19 receiving standard of care therapy. The study design is summarized in Figure 1.

Figure 1. Study Design Schematic

Abbreviations: AE = adverse event; DRC = Data Review Committee; POC = proof-of-concept; TID = three times daily.

The study is planned to include 2 parts as described below.

Part 1

Part 1 will be a 2-step dose escalation that includes approximately 60 subjects. Part 1, Step 1 will include approximately 30 subjects, and Part 1, Step 2 will include approximately 30 subjects. Part 1 will primarily focus on safety; however, efficacy data will be collected and analyzed as well.

Part 1, Step 1: For subjects enrolled in Part 1, Step 1, 6 sentinel subjects will be randomized to receive either razuprotafib 10 mg TID, razuprotafib 20 mg TID, or placebo TID (ie, 2 subjects will receive razuprotafib 10 mg TID, 2 subjects will receive razuprotafib 20 mg TID, and 2 subjects will receive placebo TID). The DRC will convene to recommend if continuation of Part 1, Step 1 as planned is acceptable or if dosing modifications are required once adverse event (AE) information through at least 8 hours following the first dose of study drug is available for all 6 sentinel subjects.

If it is decided that Part 1, Step 1 should proceed as planned, then approximately 24 subjects will be randomized to 1 of 3 treatment groups (razuprotafib 10 mg TID, razuprotafib 20 mg TID, or placebo TID) in a 1:1:1 ratio according to a computer-generated randomization list and stratified by disease severity. Subjects with moderate COVID-19 will comprise a maximum of

approximately 50% of the subjects enrolled in Part 1, Step 1. After the last subject enrolled in Part 1, Step 1 completes the Treatment Period, the Data Review Committee (DRC) will convene to review available safety and pharmacokinetic (PK) data as defined in the DRC Charter.

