2.2.2 Randomization and Blinding

After eligibility is determined, 30 subjects (6 sentinel subjects) will be randomized in a 1:1:1 ratio to 1 of the treatment groups in Part 1, Step 1:

- Razuprotafib 10 mg TID;
- Razuprotafib 20 mg TID; or
- Placebo TID.

If the Data Review Committee (DRC) recommends that Part 1, Step 2 should proceed as planned, then another 30 subjects (6 sentinel subjects) will be randomized in a 1:1:1 ratio (or a 2:1 ratio if only 1 razuprotafib dose level is chosen) to 1 of the treatment groups in Part 1, Step 2:

- Razuprotafib 20 mg TID;
- Razuprotafib 30 mg TID; or
- Placebo TID (the placebo volume will match the active volume for each treatment group).

Note: The planned dosing for Part 1, Step 2 may be changed after the DRC reviews the safety and PK data from Part 1, Step 1.

Based on the DRC's review of the available safety and PK data from Part 1, Step 1 and Part 1, Step 2, the study will proceed to Part 2. In Part 2, 120 subjects will be randomized to 1 of the treatment groups (dose 1 razuprotafib TID, dose 2 razuprotafib TID [optional], or placebo TID) in a 1:1:1 ratio (or a 2:1 ratio [razuprotafib:placebo] if only 2 treatment groups). The dosage(s) for Part 1, Step 2 and Part 2 are contingent upon DRC recommendation.

Subjects will be randomized using the centralized randomization system, according to a computer-generated randomization list, and stratified by disease severity. Sentinel subject

randomization will not be stratified by disease severity. Treatment group assignment will be blinded to subjects, clinicians, Sponsor study team, Contract Research Organization (CRO) study team, and Investigators. Specific individuals from the bioanalytical CRO and Sponsor's PK group will have access to the randomization code to allow for ongoing analysis of bioanalytical samples from the subjects treated with razuprotafib and to provide PK analysis results for the DRC reviews.

2.2.3 *Study Drug*

The drug product formulation contains AKB-9778-sodium salt ready to dose, preservative free, isotonic, sterile solution (20 mg/mL or 40 mg/mL) in a 3 mL borosilicate vial fitted with a 13 mm septum and aluminum flip top seal. Placebo for razuprotafib (sterile normal saline) will be sourced locally by the site as a parenteral formulation ready to dose.

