3.4 Efficacy Assessment

All efficacy analysis will be performed using the ITT Population. Selected endpoints will be repeated on the FA and PP Populations. In addition, the efficacy analyses will be analyzed for pooled razuprotafib doses and placebo.

Additional analyses to understand safety and efficacy variables further may be carried out and will be labeled as post-hoc analyses.

3.4.1 *Efficacy Endpoints*

The following parameters will be analyzed using Cochran-Mantel-Haenszel (CMH) test stratified by disease severity:

- Proportion of subjects alive and free of respiratory failure at Day 28;
- Proportion of subjects alive and free of respiratory failure at Day 7;

All results will be summarized descriptively by treatment arm and expressed as proportions, along with corresponding 95% CI of the difference between response rates, and p-values. The 95% CI will be constructed using the normal approximation method.

Additional Analysis may be considered by incorporating other covariate adjustments into the analysis.

Respiratory failure will be defined as subjects who are on invasive mechanical ventilation; are receiving oxygen delivered by high-flow nasal cannula (heated, humidified, oxygen delivered via reinforced nasal cannula at flow rates >20 L/min with fraction of delivered oxygen ≥ 0.5) noninvasive positive pressure ventilation or extracorporeal membrane oxygenation; or have a

clinical diagnosis of respiratory failure (ie, clinical need for 1 of the preceding therapies, but preceding therapies not able to be administered in setting of resource limitation). Subject who die prior to the study timepoint (Day 7 or Day 28) will be imputed based on the worst outcome. Other missing responses will be imputed using a multiple imputation (MI) method under the assumption of missing at random (MAR).

Sensitivity Analysis

- All missing responses will be considered as non-responders and which will be imputed taking the worst case approach.
- The analysis will be repeated on FA and PP Populations.

The following parameters will be analyzed using the CMH test as stated above:

- Proportion of subjects alive and not requiring invasive mechanical ventilation at any time through Day 28;
- Proportion of subjects who improve by ≥ 2 categories on the NIAID 8-point ordinal scale from baseline to Day 7 and baseline to Day 28;
- Proportion of subjects who worsen by ≥ 2 categories on the NIAID 8-point ordinal scale from baseline to Day 7 and baseline to Day 28;

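### In Part 1, the SAP's normal-approximation 95% CI for binary endpoints under-covers, and it is [0, 0] when both arms are at 0% or both at 100%

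*SAP*

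**What the plan says.** SAP 3.4.1 tests the two endpoints of being alive and free of respiratory failure (Day 28 and Day 7) with a CMH test stratified by disease severity. Results are to be "summarized descriptively by treatment arm and expressed as proportions, along with corresponding 95% CI of the difference between response rates, and p-values". The interval method is one sentence: "The 95% CI will be constructed using the normal approximation method". No variance form, continuity correction, stratified version or sparse-data rule is given.

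The other binary endpoints (no invasive ventilation, two-category improvement or worsening, mortality, discharge free of respiratory failure) are introduced with "The following parameters will be analyzed using the CMH test as stated above". That they inherit the same interval is an inference from those last three words. Deaths count as the worst outcome, and other missing responses are multiply imputed under missing at random. SAP 3.1.5 sets two-sided alpha at 0.05.

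Arm sizes come from SAP 2.2.2. In Step 1, "30 subjects (6 sentinel subjects) will be randomized in a 1:1:1 ratio to 1 of the treatment groups in Part 1, Step 1"; for Step 2, "then another 30 subjects (6 sentinel subjects) will be randomized in a 1:1:1 ratio", or 2:1 if only one dose is tested. Protocol 3.1 says: "Part 1 will primarily focus on safety; however, efficacy data will be collected and analyzed as well". SAP 3.4 adds: "In addition, the efficacy analyses will be analyzed for pooled razuprotafib doses and placebo". Neither document says whether Part 1 efficacy is shown by step or combined over steps.

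**The concern.** The unpooled normal approximation estimates each arm's variance from its own observed proportion. With 10 subjects per arm that estimate is noisy, and it is exactly zero at 0% or 100%. Two consequences follow. An interval labelled 95% covers less than that over most of the plausible range. And a row such as 0/10 v 0/10, quite possible for Day 7 mortality or two-category worsening, would be printed with a CI of [0, 0], which claims certainty from 20 subjects.

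The interval is also reported beside a CMH p-value, so one table row can show a CI that excludes zero and a p-value above 0.05. Only the binary efficacy contrasts are affected; the ANOVA and Kaplan-Meier endpoints are not. Dose selection rests on safety and PK, so what is at stake is the stated precision of these contrasts.

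**Working it through.** **Inputs.** Each step has 30 subjects at 1:1:1, so 30/3 = 10 per arm. By step, each dose v placebo is 10 v 10, and both doses v placebo (or a single-dose Step 2) is 20 v 10. If the steps are pooled, placebo has 10 + 10 = 20, the 20 mg group 10 + 10 = 20, the 10 mg and 30 mg groups 10 each, and all doses 40. Part 2 is 40 v 40, or 80 v 40 with one dose or pooled doses. z = 1.96. The documents give no response rates, so all rates below are assumptions.

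**Formulas.** Normal approximation: p1 - p2 ± 1.96·√[p1(1-p1)/n1 + p2(1-p2)/n2]. Newcombe: with Wilson limits (l, u) per arm, lower = p1 - p2 - √[(p1-l1)² + (u2-p2)²] and upper = p1 - p2 + √[(u1-p1)² + (p2-l2)²].

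**Example, 10/10 v 7/10.**
- Normal approximation: SE = √(0 + 0.7·0.3/10) = 0.145; 0.30 ± 0.284 = +1.6 to +58.4 points.
- Newcombe: Wilson limits are 0.722 to 1 and 0.397 to 0.892. Lower = 0.30 - √(0.278² + 0.192²) = -3.8 points; upper = 0.30 + 0.303 = +60.3 points.
- Unstratified Mantel-Haenszel: (10 - 8.5)²/[10·10·17·3/(20²·19)] = 2.25/0.671 = 3.35, p = 0.067.

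So the planned interval excludes zero while the test does not reject. At 10 v 10 the planned interval excludes zero and Newcombe includes it in 12 of the 121 possible outcomes, with Mantel-Haenszel p from 0.057 to 0.075.

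**The plan's figure is 95%.** Summing binomial probabilities over every outcome does not reproduce it:

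| Arms | False exclusion of zero, common rate 20-80%: normal v Newcombe | Mean coverage of normal approximation, both rates 20-80% |
|---|---|---|
| 10 v 10 | 9.2% v 3.8% | 91.6% (minimum 87.3%) |
| 10 v 20 or 20 v 10 | 8.2% v 4.7% | 91.7% |
| 20 v 20 | 7.3% v 4.9% | 93.5% |
| 40 v 20 | 6.3% v 5.0% | 93.4% |

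Newcombe's mean coverage in these rows is 94.5-94.8%.

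**Outside that range.** Coverage falls further when rates are unequal and near 0% or 100%: at 10 v 10, 87.5% at 10% v 20% and 75.3% at 5% v 10%; at 20 v 20, 85.8% at 5% v 10%. At equal low rates there is no shortfall (10 v 10: 98.6% at 5%, 95.0% at 10%).

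**Zero width.** With common rate p, the chance of [0, 0] is p^(n1+n2) + (1-p)^(n1+n2). At 10 v 10 this is 0.8²⁰ + 0.2²⁰ = 1.2% at 20% or 80%, and 0.9²⁰ = 12.2% at 10% or 90%. At 20 v 20 it is 0.9⁴⁰ = 1.5% at 10% or 90%.

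**Width is not the complaint in general.** At 10 v 10 the planned interval is shorter than Newcombe in 48 of 121 outcomes, and wider whenever both arms have 3-7 responders.

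**Allowing for severity.** Assume 5 moderate and 5 severe per arm, no effect, and the response rates shown. The clash column is the percentage of trials in which the CI excludes zero but the stratified CMH p is 0.05 or more.

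| Moderate/severe rate | Coverage, normal approximation | Clash: normal v Newcombe |
|---|---|---|
| 50%/50% | 91.2% | 4.5% v 0.0% |
| 80%/50% | 92.3% | 3.6% v 0.0% |
| 90%/60% | 92.6% | 2.6% v 0.0% |
| 90%/30% | 96.6% | 0.8% v 0.0% |

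**Multiple imputation.** A simulation at 10 v 10 (assumed: 10% missing completely at random, 20 Jeffreys imputations, 20,000 replicates) gave normal-approximation coverage of 91.6% at 50% v 50%, 92.5% at 80% v 80%, 89.2% at 90% v 80% and 92.1% at 90% v 95%. Imputation noise softens the sparse-rate shortfall but does not remove it.

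**Part 2.** False exclusion is 5.4% at 40 v 40 and 5.9% at 80 v 40, and mean coverage is about 94.3%. At 2% v 5% coverage is about 86% at 40 v 40; at 80 v 40 it is 86.6% with the 2% rate in the larger arm and 95.8% the other way round.

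**The case against.** The strongest reply concerns weight and remedy; the arithmetic is not in dispute. Part 1 is mainly about safety, has no formal sample-size basis, and a CMH p-value accompanies each interval. All rates are assumed, and exact 5 + 5 severity balance is idealised, since 6 of the 30 subjects per step are sentinels randomised without stratification. The SAP may have meant another variance form, and varying imputations would prevent an exact [0, 0].

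Nor does Newcombe settle agreement with the test. Counting clashes in both directions, the four severity cases give 4.5% v 0.2%, 3.9% v 1.6%, 2.8% v 2.7% and 2.8% v 3.7% (normal approximation v Newcombe): better in two, level in one, worse in one. With an assumed effect the direction also varies: 5.2% v 10.1% at 95%/60% v 90%/30%, but 9.5% v 5.4% at 90%/60% v 70%/30%. In the four null cases Newcombe over-covers (95.8%, 97.1%, 97.5%, 99.1%). Other score-type or adjusted intervals would serve: at 10 v 10 with rates of 5-95%, minimum coverage is 90.9% for Newcombe, 92.5% for Miettinen-Nurminen and 93.0% for Agresti-Caffo.

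These points stand as limits on the gain. They do not rescue the current sentence. It names no variance form, so it needs rewriting on any reading. Imputation helps only if responses are missing and the imputed values vary. A safety focus does not make an interval labelled 95% correct when the SAP commits to reporting it.

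**Conclusion.** The concern holds. On the ordinary reading of the sentence, false exclusion of zero at Part 1 sizes runs from 6.3% (40 v 20) to 9.2% (10 v 10) at common rates of 20-80%, where 5% is nominal. The interval has zero width when both arms are at 0% or both at 100%. The result rests on assumed response rates, on the unpooled, unstratified form without continuity correction, and, outside the imputation simulation, on complete data. The size depends on whether the steps are pooled, which the SAP leaves open. There is no shortfall at equal low rates or where severity strongly separates outcomes (90%/30%). The sentence should be changed, but nothing in the trial's decisions turns on it and Part 2 is nearly unaffected.

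**What to change.** Replace the interval sentence in SAP 3.4.1 with:

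> For all binary efficacy endpoints, the 95% CI for the difference in proportions will be the unstratified Newcombe hybrid-score interval; the p-value remains from the CMH test stratified by disease severity.

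Add, for multiple imputation:

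> Wilson limits per arm will be computed from the Rubin-pooled proportion p and its effective sample size p(1-p)/T, where T is the Rubin total variance, using the actual arm size when p is 0 or 1, and combined by Newcombe's formula.

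In the imputation simulation above, this interval covered 94.5%, 97.7%, 98.2% and 99.6% at the same four rate pairs. The 0-or-1 rule was needed in 0.3% to 43.7% of replicates. That check covers only 10 v 10 with 10% missing completely at random.

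**Cost.** Two SAP sentences and a little programming. Newcombe is conservative when events are sparse (99.5% at 5% v 10%, 10 v 10) and is not exact: at 10 v 10 its minimum coverage is 92.1% with both rates 20-80%, and 87.9% with both rates 2-98%. Because the interval is unstratified and the test stratified, CMH p below 0.05 can sit beside an interval that includes zero, in 0.2%, 1.6%, 2.7% and 3.7% of null trials in the four severity cases. Mid-range intervals become narrower (5/10 v 5/10: ±37.3 instead of ±43.8 points). Part 2 results barely change. It would also help to state whether Part 1 efficacy is presented by step or combined.

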4.2 Exclusion Criteria

Subjects who meet any of the following criteria will be excluded from participation in the study:

1. Inability to initiate study drug within 12 hours after randomization;
2. Female of childbearing potential who is unable or unwilling to forego breastfeeding through Day 28;
3. Systolic blood pressure < 100 mmHg;
4. In shock or requiring pressor support;
5. Subjects who are on invasive mechanical ventilation; are receiving oxygen delivered by extracorporeal membrane oxygenation (ECMO); or have clinical need for 1 of the preceding therapies, but preceding therapies not able to be administered in setting of resource limitation;
6. Alanine aminotransferase (ALT) or aspartate aminotransferase (AST) $> 3 \times$ the upper limit of normal (ULN);
7. Total bilirubin $> 2 \times$ ULN;
8. Estimated glomerular filtration rate < 30 mL/min or receiving hemodialysis or hemofiltration;
9. Moribund subject not expected to survive 24 hours in the opinion of the treating clinical team;
10. Any concurrent serious medical condition (eg, active malignancies on chemotherapy, post-organ transplant, end stage congestive heart failure) or not likely to respond to treatment;
11. Decision to withhold life-sustaining treatment;

Note: In the event of cardiac arrest, the decision to withhold cardiopulmonary resuscitation only does not fulfill this exclusion criterion.

12. Use of sensitive substrates of cytochrome P450 (CYP) 2C8 (eg, repaglinide, paclitaxel, or cerivastatin);
13. Use of CYP2C8 inhibitors (eg, gemfibrozil, fluvoxamine, or ketoconazole);
14. Participation in another investigational study during the present study through the last visit (Day 28); or
15. Previous randomization in this study.

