5.6.3 Documentation of Prior and Concomitant Medication Use and/or Procedures

Any therapies that are being used for other non-COVID-19 indications but may have an impact on SARS-CoV-2 and COVID-19 (eg, IL-6 inhibitors or hydroxychloroquine for rheumatological conditions) should be listed as concomitant medication along with the time, dose, and duration of their administration.

Any treatment given in addition to the study drug during the study is regarded as a concomitant medication and must be recorded on the appropriate eCRF.

Any relevant medications received in the 14 days prior to study drug administration must be recorded on the appropriate eCRF, along with the reason for use, dates of administration, and dosages.

Concomitant medications should be kept to a minimum during the study. However, if these are considered necessary for the subject's welfare, are unlikely to interfere with the study drug, and not specifically excluded, then they may be given at the discretion of the Investigator and recorded in the subject's source documents and the eCRF. Investigators are encouraged to discuss specific medications with the Medical Monitor or Sponsor when in question.

Any care decisions that are made due to resource limitation (eg, ventilation not available) must be documented.

Data surrounding major changes in background therapy will be collected. The standard of care that is followed for each subject and site must be recorded. If standard of care therapies are not able to be delivered due to resource limitations, this should also be recorded.

Any reasons for discontinuation of ventilation must be recorded on the appropriate eCRF, including all data related to clinical decision making that guides removal from mechanical ventilation in relation to clinical deterioration or lack of clinical response.

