2.3 Study Endpoints

2.3.1 *Efficacy Endpoints*

The efficacy endpoints include the following:

- Proportion of subjects alive and free of respiratory failure at Day 28;
- Proportion of subjects alive and free of respiratory failure at Day 7;
- Proportion of subjects alive and not requiring invasive mechanical ventilation at any time through Day 28;
- Time to reach grade 6, 7 or 8 on the NIAID 8-point ordinal scale;
- Change in PaO₂:FiO₂ ratio from baseline to Day 7 (or discharge) and baseline to Day 28 (or discharge);

- Length of hospitalization and not requiring invasive mechanical ventilation from baseline to Day 7 and baseline to Day 28 or death;
- Length of hospitalization from baseline to Day 7 and baseline to Day 28 or death;
- Proportion of subjects who improve by ≥ 2 categories on the National Institute of Allergy and Infectious Diseases (NIAID) 8-point ordinal scale from baseline to Day 7 and baseline to Day 28;
- Proportion of subjects who worsen by ≥ 2 categories on the NIAID 8-point ordinal scale from baseline to Day 7 and baseline to Day 28;
- All-cause mortality at Day 7 and Day 28;
- Number of subjects in each category of the NIAID 8-point ordinal scale at Day 7 and Day 28;
- Time to return to prehospitalization oxygen requirement; and
- Proportion of subjects who were discharged and remained free of respiratory failure prior to Day 7 and Day 28.

The NIAID 8-point ordinal scale includes the following grades:

1. Death;
2. Hospitalized, on invasive mechanical ventilation or Extracorporeal membrane oxygenation (ECMO);
3. Hospitalized, on noninvasive ventilation or high-flow oxygen devices;
4. Hospitalized, requiring supplemental oxygen;
5. Hospitalized, not requiring supplementation oxygen – requiring ongoing medical care (COVID-19 related or otherwise);
6. Hospitalized, not requiring supplemental oxygen – no longer requires ongoing medical care;
7. Not hospitalized, limitation on activities and/or requiring home oxygen; and
8. Not hospitalized, no limitations on activities.

2.3.2 *Pharmacodynamic (PD) and Pharmacokinetic (PK) endpoints*

The PD and PK endpoints include in the following:

- Change from baseline in CRP and D-dimer;
- Change from baseline in systemic biomarkers of vascular leakage and inflammation (ie, Angpt-2, IL-6, IL-8, TNF α , and HMGB-1);
- Summary of plasma concentrations of biomarkers at each sampling time point for each treatment group; and

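### The respiratory-failure definition counts unmet need for support only under resource limitation, so a living subject on no listed support after a decision to limit care is scored as a responder

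*SAP*

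**What the plan says.** SAP 3.4.1 tests "Proportion of subjects alive and free of respiratory failure at Day 28", and the same proportion at Day 7, with a CMH test stratified by disease severity. The definition that drives both begins "Respiratory failure will be defined as subjects who are on invasive mechanical ventilation". It goes on to high-flow nasal oxygen above stated thresholds, noninvasive positive pressure ventilation and ECMO. Its last limb is a clinical diagnosis of respiratory failure, introduced by an ie and confined to "clinical need for 1 of the preceding therapies, but preceding therapies not able to be administered in setting of resource limitation". The Population section of the Protocol Synopsis gives the same definition.

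On deaths, SAP 3.4.1 states "Subject who die prior to the study timepoint (Day 7 or Day 28) will be imputed based on the worst outcome". Other missing responses go to multiple imputation under missing at random. The sensitivity analyses set missing responses to non-response and repeat the analysis on the FA and PP Populations.

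Two protocol passages touch on limits to care:

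- Protocol 4.2, criterion 11, excludes subjects with a "Decision to withhold life-sustaining treatment". Its note does not apply this to a decision that covers cardiopulmonary resuscitation only.
- Protocol 5.6.3 requires the eCRF to hold the reasons for stopping ventilation, "including all data related to clinical decision making that guides removal from mechanical ventilation in relation to clinical deterioration or lack of clinical response".

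**The concern.** The definition accepts that a subject who needs a listed support and does not get it is in respiratory failure, but only when the cause is a shortage of resources. A subject in the same respiratory state who lacks support because of a decision to limit care falls outside it. The reason for the missing support then decides whether the subject is a failure or a success, although respiratory status is the same.

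Such decisions usually follow deterioration, so the misscoring is related to outcome and need not balance between arms. In arms as small as these, one or two subjects matter. Protocol 5.6.3 shows that removal of ventilation for deterioration or lack of response was foreseen, yet no scoring rule in the SAP uses that information.

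**Working it through.** The documents give no response rate, effect size or frequency of care-limitation decisions, so there is no stated figure to reproduce. The check has two parts: apply the rule as written, then find what one subject is worth.

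**1. Applying the rule.** The cases are hypothetical. All subjects are alive at Day 7.

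| Case | Listed support at timepoint? | Resource limitation? | Day 7 score |
|---|---|---|---|
| A. Intubation declined, still on qualifying high-flow oxygen | Yes | Not relevant | Failure |
| B. Needs ventilation, none available | No | Yes | Failure |
| C. On qualifying high-flow oxygen on Day 5, comfort care on ordinary nasal cannula from Day 6, dies Day 9 | No | No | Success (Day 28: failure, by death) |
| D. Discharged to hospice on Day 6, on no listed support | No | No | Success |

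Case D takes the Day 7 response from the discharge-day record. Protocol Appendix A, footnote c, puts the Day 7 procedures on the day of discharge, and SAP 3.1.3 analyses nominal visits. Case D can also meet the endpoint of discharge while remaining free of respiratory failure.

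**2. Does another rule catch cases C and D?**

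- Death rule (SAP 3.4.1): no. It needs death before the timepoint.
- Multiple imputation, and the sensitivity analysis that sets missing to non-response: no. The response is observed.
- FA and PP repeats: no. They change who is analysed, not how a subject is scored.
- Weaning rule (Protocol 7.1): no. It counts days on and off the ventilator and does not set status after permanent withdrawal.
- Exclusion criterion 11 (Protocol 4.2): no. It applies at entry only.

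**3. Weight of one subject.** Shift in an arm's proportion = 1/n.

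- Part 2, 1:1:1 (SAP 2.2.2): n = 120/3 = 40, so 1/40 = 2.5 points.
- Part 2, 2:1: active n = 80, so 1/80 = 1.25 points; placebo n = 40, so 2.5 points.
- Part 1, one step at 1:1:1: n = 30/3 = 10, so 1/10 = 10 points.

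**4. Direction.** The counts here are assumed for illustration and are not evidence of size. The test is an unstratified two-proportion z test with pooled standard error, at the two-sided 0.05 level of SAP 3.1.5. Suppose correct scoring gives 35/40 on active and 28/40 on placebo.

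- Correct scoring: 0.875 − 0.700 = 17.5 points. Pooled p = 63/80 = 0.7875; SE = √(0.7875 × 0.2125 × 2/40) = 0.0915; z = 1.91; p = 0.056.
- One active subject wrongly scored a responder: 36/40 vs 28/40, 20.0 points, p = 0.025.
- One placebo subject wrongly scored a responder: 35/40 vs 29/40, 15.0 points, p = 0.094.

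The error can move the result either way.

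**The case against.** The strongest reply is that few subjects can be affected. The subject must be alive at the timepoint, on none of the listed supports, and under a decision to limit care made after randomization. Protocol 4.2 removes moribund subjects, those with serious concurrent conditions, and those with an existing decision to withhold life-sustaining treatment. Most of those affected at Day 7 would probably have died by Day 28. Other endpoints give partial cover: the proportion alive and never needing invasive ventilation through Day 28 counts anyone ever ventilated as a failure, and Day 28 mortality captures case C. An investigator might also read the clinical-diagnosis limb more widely.

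The point about numbers stands and limits the size. The other endpoints are separate analyses and do not correct the scoring of this one. The wide reading of the clinical diagnosis is not what the ie says, and scoring should not depend on it.

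A reader might infer more than the documents support:

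- **That any subject with a do-not-intubate decision is scored a success.** Case A shows otherwise.
- **That a post-discharge call gives a Day 6 hospice discharge a Day 7 ordinal grade of 7, and so an improvement.** Appendix A, footnote c, schedules a Day 7 call only for discharges on Days 1 through 4.
- **That the flaw falls on a designated lead endpoint.** Neither document names a primary efficacy endpoint.
- **That it predictably hides benefit or harm.** That rests on assumed rates in each arm, which the documents do not give.

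**Conclusion.** The point holds as a gap in the scoring rule. As written, SAP 3.4.1 counts as responders those subjects who are alive at the timepoint and on no listed support because needed support was withheld or withdrawn under a decision to limit care. No other rule in either document re-scores them. The effect falls mainly on the Day 7 endpoint and on the discharge endpoint that uses the same definition.

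The weight per subject follows from the planned arm sizes. The number of subjects is unknown and probably small, and the net direction cannot be stated in advance. The conclusion assumes that the ie in the definition is exhaustive and, for subjects discharged before Day 7, that the discharge-day record supplies the Day 7 response.

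It does not follow that hospice discharge must take the worst outcome on the ordinal improvement and recovery endpoints. That is one composite choice among several, and it is separate from this gap.

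**What to change.** Before unblinding, extend the last limb of the definition in SAP 3.4.1. It should cover clinical need for a listed therapy that is not given, or is withdrawn, because of resource limitation or a decision to limit care. These subjects then become non-responders on the respiratory-failure endpoints. If the sponsor prefers to keep the present definition for the main analysis, the wider scoring should at minimum be a pre-specified sensitivity analysis. The SAP would then differ from the Protocol Synopsis, so the change belongs in SAP section 6.

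For identification, use the Protocol 5.6.3 record where a ventilator was removed. That record does not name step-down from high-flow oxygen, support that was never started, or discharge to hospice, so those cases need a site query made blind to treatment.

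The cost is a wording change, an entry in section 6 and probably a few queries. Only endpoint scoring changes; no treatment or care decision is affected.
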